6.3 Characteristics of patients at baseline and comparison

Description of the demographics and baseline characteristics will be presented in **Table 3** by randomized groups (wedges), and then perform the significance test among 4 groups using **linear regression with generalized estimating equations (GEE) for continuous variables and logistic regression with GEE for category variables** (GEE to adjust for clustering within hospitals) to see if there is any imbalance among randomized groups (, or speak, among groups initiating the intervention at different time). The continuous variables will be presented as means and standard deviations, or medians and inter-quartile range, as appropriate.

Description of the demographics and baseline characteristics by cycle will be presented in **Table 3.1**.

Description of the demographics and baseline characteristics by intervention and control will also be presented (**Table 4**), and test the statistical significance of each variable.

6.4 Main efficacy analyses for the primary outcome

Simple description of primary outcome

The raw percentage of in-hospital MACE will be summarized as n (%) **by wedge and cycle** (**Table 5**) **and by intervention and control** (**Table 5.1**).

Model analysis for primary outcome

In a stepped wedge design more clusters are exposed to the intervention towards the end of the study than in its early stages (one-way). This implies that the effect of the intervention might be confounded with any underlying temporal trend. A result that initially might seem suggestive of an effect of the intervention may therefore transpire to be the result of a positive underlying temporal trend, or vice versa. [reference 2] That means we will **adjust for time in primary analysis**.

The primary analysis will use generalized estimating equations (GEE), an extended form of logistic regression, to compare the odds of in-hospital MACE between intervention and control using all periods' data. Cycle (every 6 months) will be taken as a **fixed effect**, with an **exchangeable correlation structure** to account for clustering (the correlation within hospitals). [reference 3] A robust standard error will be used to guard against misspecification of the correlation structure.

Model 1

Firstly, we will fit a model (**Model 1**) in which we will include the main effect of intervention only,

$$\text{Logit}(p_i) = \beta_0 + \beta_1 \text{Intervention} + e_i$$

Where e_i means the random error in i th patient.

Then, we will examine if there is a time effect in the following two ways:

Model 2 (primary analysis)

Assuming the time effect is non-linear, we will include the main effect of intervention and time (cycle) into Model 2, with cycle treated as a categorical variable (with the first cycle as the reference category) to test if there is a significant intervention effect after adjusting for the time effect.

The log odds of MACE in Model 2 for the i th patient can be written as:

$$\text{Logit}(p_i) = \beta_0 + \beta_1 \text{Intervention} + \beta_2 \text{cycle2} + \beta_3 \text{cycle3} + \beta_4 \text{cycle4} + \beta_5 \text{cycle5} + e_i$$

Model 3

Assuming the time effect is linear, we will include the main effect of intervention and time (cycle) into Model 3, with cycle treated as a continuous variable. The log odds of MACE in Model 3 for i th patient can be written as:

$$\text{Logit}(p_i) = \beta_0 + \beta_1 \text{Intervention} + \beta_2 \text{cycle} + e_i$$

The model 2 and 3 will be done whatever the main effect of intervention in Model 1 will be significant or not.

Model 4

If there is no significant time effect in Model 2 and 3, Model 4 won't be conducted.

If there is a significant time effect, either in Model 2 or 3, we will fit a full model with a time*intervention interaction term, in which the interaction between intervention and time will be tested to see if there is an additional effect over time after initiating the intervention. The probability of MACE in Model 4 for i th patient then can be written as:

$$\text{Logit}(p_i) = \beta_0 + \beta_1 \text{intervention} + \beta_2 \text{time} + \beta_3 \text{intervention} * \text{time} + e_i$$

With time as a categorical or continuous variable.

In case of an additional effect of time does not exist, the interaction term will be removed from this model, that is, return to Model 2 and 3.

Adjusting for potential confounders at patient level and hospital level:

All models will have unadjusted analysis and adjusted analysis for the patient-level covariates or hospital-level covariates to account for the potential confounding from baseline characteristics. All adjusted analyses will be considered as secondary. Three-level generalized linear-mixed models with hospital and province as second and third levels, respectively, will be used in the adjusted analysis. Exploratory analysis on covariates (eg. univariate modeling,

scatter plot) will be conducted and only those that are either significantly associated with the outcomes ($P < 0.05$) or have strong clinical importance will be further added to the model. Potential interaction terms between them will be also examined similarly afterwards.

The resulting odds ratios of all the **fixed effects** from the Model 1 to Model 3 (unadjusted and adjusted), as well as their 95% CIs, will be reported along with their respective p-values in **Table 6 to Table 8**.

In the rare case that the GEE models do not converge, the **Quadratic Inference Function (QIF)** [reference 4] will be used as an alternative approach. Unlike GEE, the estimator function of QIF is bounded and approaches zero, so the QIF estimator improves the efficiency of GEE when the working correlation is misspecified and remains as efficient as GEE when the working correlation is correct.

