CPACS-3 study is a stepped-wedge cluster-randomized trial conducted in 104 resource-constrained hospitals from 15 provinces in China. Patients with acute coronary syndromes (ACS) will be recruited consecutively, with an anticipated total of 25,000 patients recruited within 30 months. All eligible hospitals will be randomised (stratified by province) to 4 wedges. Each wedge contains 26 hospitals. During the first 6 months data will be collected from all hospital participants without any intervention being implemented. Afterwards, the intervention will be implemented sequentially, starting with the first group of 26 hospitals (wedge 1). The second group of hospitals (wedge 2) will start the intervention 12 months later and wedges 3 and 4 will start the intervention at 18 and 24 months later respectively: see Figure 1. By 30 months, all hospitals would have had the intervention implemented for at least 6 months and final data will be collected at this time.

[figure not shown]
The intervention will be applied at the level of the hospital, with outcomes measured at the patient level. The ACS quality of care improvement initiative includes six components:

1. Leadership strengthening and establishment of QCI leaders group
2. Implementation of clinical pathway

3. Hospital performance audit and feedback
4. Training of physicians and nurses
5. Online technical support, and
6. Patient education

All patients discharged alive from hospital will be followed up 6 months later by telephone call.

Figure 1. Visual representation of the stepped wedge design used in CPACS 3

3 Evaluation Outcomes

Primary outcome

The primary outcome is in-hospital major adverse cardiovascular events (MACE), a composite outcome including all-cause mortality, myocardial infarction or re-infarction and stroke. The in-hospital all-cause mortality include patients who died in hospital, those who gave up treatment but died within 1 week after returning home, and those who transferred to upper level hospitals but died within 24 hours.

Secondary outcome

The following secondary endpoints will be considered:

- 1) In-hospital all-cause deaths.
- 2) A patient-level composite score is formed by dividing the total number of pre-defined binary key performance indicators (KPIs) a patient receives (numerator) by the total sum of KPIs a patient is eligible to receive (denominator). However, the length of stay will not be used for the calculation of the composite score.

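### The primary Model 2 leaves out province, the factor that stratified the randomisation, so a modest amount of precision goes unused; the primary test remains valid

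*SAP*

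**What the plan says.** SAP section 2 describes the trial as "conducted in 104 resource-constrained hospitals from 15 provinces in China" and states: "All eligible hospitals will be randomised (stratified by province) to 4 wedges". It adds: "Each wedge contains 26 hospitals".

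Section 6.4 names Model 2 as the primary analysis. It is a logistic GEE with an exchangeable correlation within hospitals, and "we will include the main effect of intervention and time (cycle) into Model 2". The written equation has an intercept, the intervention indicator and four cycle indicators. On the standard error it says: "A robust standard error will be used to guard against misspecification of the correlation structure".

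Province comes in later in section 6.4, as the third level of the generalized linear mixed models used for covariate adjustment. Of these the SAP says: "All adjusted analyses will be considered as secondary". Sections 6.5 to 6.8 carry Model 2 over to the secondary outcomes, again without province. No reason is given for leaving it out.

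**The concern.** Stratifying by province makes the wedges nearly balanced within each province, so differences in event rate between provinces largely cancel out of the intervention estimate. An analysis that ignores province does not use that balance. Between-province variation stays in the residual, the GEE weights are chosen as if it were ordinary hospital variation, and a sandwich estimator clustered on hospital treats it as noise. Putting the stratification factor in the model is the usual way to recover that precision.

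The stake is efficiency. Precision matters here because the cycle-adjusted primary model has less power than section 4 states (see the working), although that shortfall is a separate matter. The choice also has to be made in advance: section 1 requires the SAP to be final before any unblinded analysis, and adding province afterwards would be post hoc.

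**Working it through.** **Inputs.** From section 4: 96 hospitals, 40 patients per hospital per cycle, control rate 8%, relative reductions of 20% and 15% (risk differences 0.016 and 0.012), ICC 0.10, alpha 0.05. From section 6.1: two-sided tests. From section 2: 4 wedges, 15 provinces. From section 6.4: 5 cycles. I take the wedges to cross over at cycles 2, 3, 4 and 5. All figures are linear-scale approximations.

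**Notation.** I = 96 and T = 5. The treated hospital-cycles number U = 24 × (4+3+2+1) = 240. The squared column totals sum to W = 24² × (0+1+4+9+16) = 17,280. The squared row totals sum to V = 24 × (16+9+4+1) = 720.

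**Step 1: the SAP's own power.** Use the average rate 0.072 for a 20% reduction, hospital clustering and no cycle effects.
- Total variance is 0.072 × 0.928 = 0.066816, so σ² = 0.9 × 0.066816/40 = 0.001503 and τ² = 0.006682.
- Generalised least squares gives SE = 0.003936 and power Φ(0.016/0.003936 − 1.96) = 98.2%.
- The same calculation for 15% gives 85.3%. The stated 98% and 85% are reproduced.

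**Step 2: add the cycle effects of Model 2.** With control-rate variance 0.08 × 0.92 = 0.0736, σ² = 0.001656 and τ² = 0.00736.

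Var = Iσ²(σ² + Tτ²) / [(IU − W)σ² + (U² + ITU − TW − IV)τ²]

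= 96 × 0.001656 × 0.038456 / [5,760 × 0.001656 + 17,280 × 0.00736] = 0.0061136/136.72 = 4.472 × 10⁻⁵, so SE = 0.006687.

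Power is 66.7% and 43.4% (70.9% and 46.0% with average-rate variance). This is a different and larger issue than province.

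**Step 3: why province can help only a little at ICC 0.10.** If only within-hospital contrasts were used (τ² → ∞), Var = ITσ²/17,280 = 96 × 5 × 0.001656/17,280 = 4.600 × 10⁻⁵. The ratio 4.472/4.600 = 0.97 shows that about 97% of the information in Model 2 is within-hospital. Province does not change over time, so it drops out of those contrasts.

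**Step 4: add province.** Split the hospital variance into a province share f (assumed, as the SAP gives none) and the remainder, with wedges nearly balanced within 15 provinces. The gain is 1 − (SE with province)/(true SE without).

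| ICC | f | True SE, no province | SE with province | Gain |
|---|---|---|---|---|
| 0.10 | 0 | 0.006687 | 0.006691 | −0.1% |
| 0.10 | 0.25 | 0.006670 | 0.006662 | 0.1% |
| 0.10 | 0.50 | 0.006653 | 0.006609 | 0.7% |
| 0.10 | 0.75 | 0.006636 | 0.006473 | 2.5% |
| 0.01 | 0 | 0.006438 | 0.006460 | −0.3% |
| 0.01 | 0.25 | 0.006365 | 0.006350 | 0.2% |
| 0.01 | 0.50 | 0.006282 | 0.006189 | 1.5% |
| 0.01 | 0.75 | 0.006206 | 0.005953 | 4.1% |

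A hand check with exact balance puts τ²(1 − f) into the Step 2 formula. At ICC 0.10 and f = 0.75, τ² = 0.00184, Var = 0.158976 × 0.010856/(9.539 + 31.795) = 4.175 × 10⁻⁵ and SE = 0.00646, close to the 0.006473 in the table. At f = 0.80 the same calculation gives gains of 3.3% (ICC 0.10) and just under 5% (ICC 0.01).

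**Step 5: calibration of the robust SE.** In large samples the hospital-clustered SE without province exceeds its true value by 0 to 0.8% at ICC 0.10 (0.006687/0.006636 = 1.008 at f = 0.75). An uncorrected sandwich with about 100 clusters is biased downwards by a similar amount. The expected ratio to the true SE is then 0.991 to 0.996 for f from 0.2 to 0.8, and simulation with 104 hospitals and 48 patients per cycle gave 0.97 to 1.00.

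With 14 province indicators and no correction, the ratio falls to 0.987–0.982 at ICC 0.10 and 0.975–0.966 at ICC 0.01. Type I error is 2Φ(−1.96 × 0.987) = 5.3% at the best of these and 2Φ(−1.96 × 0.966) = 5.8% at the worst. Simulation gave about 5.5 to 6%.

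**The case against.** A reader might infer that the primary confidence interval is wrong because it ignores how hospitals were allocated. The SAP does not support that. The hospital is the unit randomised, the GEE clusters on it, and the standard error is robust. Ignoring stratification errs, if at all, on the conservative side. At ICC 0.10 even that small excess is offset by the ordinary small-sample bias of the sandwich. A clear excess (4.5% in simulation) appeared only at ICC 0.01 with 80% of hospital variance between provinces.

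A reader might also infer a larger gain, such as the 7.5% between 0.006438 and 0.005953 at ICC 0.01 and f = 0.75. That comparison starts from the large-sample reported SE, not the true one of 0.006206. It therefore counts the removal of an overstatement as precision gained, and it ignores the downward bias.

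Three further objections stand:
- Province is already used in the prespecified secondary models.
- Fourteen extra terms are not trivial merely because about 2,000 events are expected (8% of 25,000). Province is a hospital-level factor, so the relevant count is 104/15, or about 7 hospitals per province, and an uncorrected sandwich becomes anti-conservative.
- On the logit scale, province terms change the odds ratio from marginal to province-conditional.

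These shape the remedy but do not remove the point. Adding the design factor costs almost nothing in precision if it proves useless, and the SAP gives no reason for omitting it. ICC 0.10 should not be the only yardstick either: at an 8% rate it implies a between-hospital SD of √(0.10 × 0.08 × 0.92) = 8.6 percentage points, larger than the mean. At ICC 0.01 the SD is 2.7 points.

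**Conclusion.** The omission is real and unexplained, and its consequence is modest. For an assumed province share of 0 to 75%, the unused precision is about 0 to 3% of the SE at the SAP's ICC of 0.10 and about 0 to 4% at ICC 0.01. At ICC 0.10 that amounts to at most about 3 power points (66.7% to 69.6% for a 20% reduction, measured from the reported SE). If provinces do not differ, nothing is gained and at most about 0.3% of the SE is lost. There is no bias and no material false-positive risk from leaving province out, and the primary test stands. Province does not cure the power shortfall of Step 2. The size rests on the assumed province share, near-balanced wedges within provinces of similar size, and a linear-scale approximation to the logistic GEE.

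**What to change.** In section 6.4, add province to Model 2 as a fixed categorical factor (14 indicators). Do the same wherever Model 2 is used for the secondary outcomes (6.5 to 6.8) and the sensitivity analyses (6.10). Keep the GEE and the exchangeable correlation. Replace the plain robust SE with a small-sample bias-corrected one, such as Kauermann-Carroll or Mancl-DeRouen, and name it. State before unblinding how provinces with too few hospitals or events will be merged. Say that the primary odds ratio is conditional on province. If the sponsor prefers to keep the marginal odds ratio without province, one sentence giving that reason would be enough.

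The cost is a short SAP amendment. Province is known for every hospital, so no new data are needed.

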6.6 Analysis for the composite score of KPIs (secondary outcome)

Based on 15 pre-defined binary KPIs, except for the length of stay, we will develop a composite score by simply sum up them with giving each KPI one score, and then normalize the score by dividing the sum by the number of eligible KPIs to the specific patient.

A simple description for the composite score by wedges and by cycles will be presented in **Table 17** (similar format to Table 5) and by intervention and control in **Table 13.1**.

Model 1 to model 4 (unadjusted and adjusted) will be applied to the composite score except that linear regression with GEE will be used instead of logistic regression with GEE for all the model analyses.

In a similar format to Table 6 to Table 8, the results of all the fixed effects from Model 1 to Model 3 (unadjusted and adjusted) for the composite score will be presented in **Table 14 to Table 16**, in which the regression coefficients will be also reported along with the odds ratios.

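### For binary outcomes the secondary adjusted analyses change from marginal GEE with a robust SE to a three-level mixed model with no stated SE method, and sections 6.6 and 6.7 contradict this

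*SAP*

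**What the plan says.** **Primary model (SAP 6.4).** "The primary analysis will use generalized estimating equations (GEE), an extended form of logistic regression, to compare the odds of in-hospital MACE". The working correlation is exchangeable within hospital, and "A robust standard error will be used to guard against misspecification of the correlation structure".

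**Adjusted versions (SAP 6.4).** "All models will have unadjusted analysis and adjusted analysis for the patient-level covariates or hospital-level covariates". The stated purpose is to allow for confounding by baseline characteristics. The model then changes: "Three-level generalized linear-mixed models with hospital and province as second and third levels, respectively, will be used in the adjusted analysis". No reason is given, and the text states neither how standard errors are obtained nor whether there is a hospital-by-cycle effect. Covariates enter after exploratory univariate work: "only those that are either significantly associated with the outcomes" at P<0.05, or judged clinically important, are kept. No list is given.

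**Status and reporting (SAP 6.4).** "All adjusted analyses will be considered as secondary". Tables 6 to 8 hold both versions: odds ratios "from the Model 1 to Model 3 (unadjusted and adjusted), as well as their 95% CIs, will be reported along with their respective p-values".

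**Other outcomes.** Section 6.6 applies Models 1 to 4, unadjusted and adjusted, to the composite KPI score and says that "linear regression with GEE will be used instead of logistic regression with GEE for all the model analyses". Section 6.7 names GEE for all 16 KPIs and also plans adjusted results, with no mention of a mixed model. Sections 6.5 and 6.8 refer back to the models of 6.4.

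**The concern.** Three things follow from the change of model family.

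- **Two estimands.** With a logit link, GEE estimates a population-average odds ratio and the mixed model an odds ratio conditional on hospital and province. They differ even with no covariates and no confounding. A reader of Tables 6 to 8 cannot tell how much of a shift is due to the covariates.
- **Unstated SE.** The SAP considers a misspecified correlation structure worth guarding against in the GEE, but specifies no guard for the adjusted models. If these have only hospital and province intercepts and model-based SEs, they assume that correlation within a hospital is constant over 30 months.
- **Contradiction.** Under 6.4 the adjusted composite-score model is a mixed model; under 6.6 it is a GEE. Two programmers could fill the same table with different models.

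In addition, covariates chosen by P<0.05 in the trial's own data leave the adjusted estimate without a fixed specification.

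**Working it through.** The plan gives no figure on this point, so there is none to reproduce. The check measures what the change of model does.

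**Inputs from the SAP.** Section 4: event rate 8%, risk reductions of 20% and 15%, 96 hospitals, 40 patients per cycle, ICC 0.10 (scale not stated). Section 6.1: two-sided α 0.05. Section 6.4: five cycles, the first as reference. Section 2: four equal wedges.

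**Assumptions.** One wedge crosses over at each cycle from cycle 2. Lower ICCs and the ratio c of between-period to within-period correlation are varied, as the SAP does not give them.

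**1. Size of the odds ratio**

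- Marginal OR, 20% reduction: (0.064/0.936)/(0.080/0.920) = 0.786, log OR −0.240.
- Marginal OR, 15% reduction: (0.068/0.932)/(0.080/0.920) = 0.839, log OR −0.175.
- Conditional OR: for each marginal rate p, solve ∫ expit(a + σz)φ(z)dz = p for a. The conditional log OR is the difference of the two a values.
- Latent scale, ICC 0.10: σ² = (0.10/0.90) × π²/3 = 0.366.
- Probability scale: σ² is chosen so that Var(p)/[0.08 × 0.92] = 0.10, which gives σ² ≈ 1.25.

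| ICC and scale | Conditional OR, 20% reduction | Log OR, conditional/marginal |
|---|---|---|
| 0.10, latent | 0.781 | 1.027 |
| 0.10, probability | 0.767 | 1.103 |
| 0.05, probability | 0.777 | 1.048 |
| 0.02, probability | 0.783 | 1.019 |
| 0.01, probability | 0.785 | 1.009 |

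For a 15% reduction at ICC 0.10, 0.839 becomes 0.835 (latent) or 0.824 (probability).

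**2. Significance.** In a simulation of the largest case (σ² = 1.25, 96 hospitals, 40 per cycle, cycle categorical, no covariates, no hospital-by-cycle variation, 150 replicates):

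- GEE with robust SE: log OR −0.240, SE 0.095, mean z −2.54.
- Mixed model: log OR −0.265, SE 0.105, mean z −2.55.

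Estimate and SE grow by the same factor: 0.265/0.240 = 1.10 and 0.105/0.095 = 1.11. Significant replicates were 65% and 67%. At σ² = 0.37 mean z was −2.44 and −2.38.

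**3. Standard error, if model-based.** This is a linear approximation with cycle categorical and 24 hospitals per wedge. Let A = ΣZ′W⁻¹Z, where W is the covariance under constant within-hospital correlation. The reported variance is the intervention element of A⁻¹. The true variance is that element of A⁻¹(ΣZ′W⁻¹VW⁻¹Z)A⁻¹, where V has correlation ICC within a cycle and c × ICC between cycles. With R = true SE/reported SE, type I error is 2[1 − Φ(1.96/R)].

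| c | R, ICC 0.10 | Type I error | R, ICC 0.02 | Type I error |
|---|---|---|---|---|
| 1 | 1.00 | 5.0% | 1.00 | 5.0% |
| 0.95 | 1.10 | 7.5% | 1.02 | 5.4% |
| 0.9 | 1.19 | 10.0% | 1.03 | 5.8% |
| 0.8 | 1.35 | 14.7% | 1.07 | 6.6% |

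For example, at ICC 0.10 and c = 0.9, 1.96/1.19 = 1.65, which gives about 10%.

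**4. Linear outcomes.** With an identity link the marginal and conditional effects coincide, so step 1 does not apply to the composite score or length of stay. What remains there is the contradiction between 6.4 and 6.6 or 6.7.

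**The case against.** The strongest reply is that the primary inference, unadjusted Model 2, keeps its GEE and robust SE, while everything adjusted is declared secondary. A second model family for secondary analyses is legitimate, and this one brings in province, the randomisation stratum, which Model 2 omits. This stands, and it limits the weight of the point.

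Other parts of the reply:

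- **Significance.** A reader might infer that the switch to a conditional odds ratio makes adjusted results more significant. Step 2 shows that it does not. Even the 10% case moves the log OR by only 0.025, about a quarter of one SE (0.025/0.095 = 0.26).
- **SE.** A reader might infer that the mixed model has no robust SE. The SAP is silent on this, and a mixed model can carry a sandwich SE. The type I errors above depend on that silence being filled by model-based SEs and on an assumed c; at c = 1 there is no loss.
- **Confounding.** The SAP sets no rule for judging confounding from the change between columns. It only reports both, although confounding is its stated reason to adjust.
- **Non-collapsibility.** Adding prognostic covariates within GEE also moves an odds ratio without confounding. A single model family reduces the mismatch but does not remove it.
- **Screening.** P<0.05 is not the only route into the model, as clinical importance also qualifies. That criterion is not defined, so the list is still open.

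The contradiction between 6.4 and 6.6 needs no assumption, and none of these replies answers it.

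**Conclusion.** The point holds as a modest defect that is cheap to correct. For binary outcomes the unadjusted and adjusted odds ratios in Tables 6 to 8 have different estimands. The gap in log OR is about 3% (latent scale) to 10% (probability scale) at ICC 0.10, and 1% to 2% at probability-scale ICC 0.01 to 0.02. It affects the size of the odds ratio, not its significance, and is absent for linear outcomes.

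The SE question may matter more but is conditional. With model-based SEs and c between 1 and 0.8, type I error of the adjusted tests would be about 5% to 15% at ICC 0.10 and 5% to 7% at ICC 0.02. The defect shown is an unspecified SE method, not a demonstrated inflation.

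The conflict of 6.4 with 6.6, and by implication with 6.7, is on the page and must be resolved. The documents do not support a reading in which the primary result is compromised.

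**What to change.** - Fit the adjusted analyses of binary outcomes with the same GEE as Model 2: logit link, exchangeable correlation within hospital, robust SE. Province can be kept as a fixed factor.
- Replace the P<0.05 screening with a covariate list fixed before unblinding, drawn from variables known at or before admission.
- If the mixed model is kept, make it a labelled sensitivity analysis. Fit it without covariates as well, state its SE method, include a hospital-by-cycle random effect, and label its odds ratio as hospital-specific.
- Make 6.4, 6.6 and 6.7 name the same model for the adjusted analyses.

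The cost is SAP wording, with one model family to program in place of two. Section 1 already requires the plan to be final before any unblinded analysis. The downside is small: adjusted and unadjusted odds ratios will still differ somewhat through non-collapsibility, which a table footnote can say.

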Three newly added KPIs	Due to the changes in clinical guidelines and clinical practice, it is appropriate to add in the following new indicators.	
Dual antiplatelet therapy	The patient received both aspirin and clopidogrel within 24 hours of arrival at hospital	All patients
Loading dose dual antiplatelet therapy	The patient received both aspirin and clopidogrel with loading dose (i.e. 300 mg or above for each medicine) within 24 hours of arrival at hospital	All patients
Loading dose statin therapy	The patient received statin with loading dose (i.e. 40 mg or above of atorvastatin or equivalent) within 24 hours of arrival at hospital	All patients

*: STEMI: ST-elevated myocardia infraction; NSTEMI: non-ST-elevated myocardia infraction; UA: Unstable angina.

4 Power

Data from our previous CPACS studies estimated the primary outcome to be 8.6% in level two hospitals and the **unadjusted and adjusted intervention effect size was 12% and 59%** [reference 1]. With an improved and better coordinated intervention in CPACS-3, we believe that an expected effect size of 15% to 20% reduction of primary outcome should be reasonable. Assuming an event rate of 8% for the primary outcome and $\alpha = 0.05$, a study with 96 hospitals and 40 patients per cycle from each hospital will provide 98% and 85% power to detect relative risk reduction of 20% and 15%, respectively in the primary outcome. The sample size calculations are based on the assumptions that there is no delay in the effect of the intervention and an **intra-class correlation coefficient of 0.10**. To account for possible drop out of participating hospitals, a total of 104 hospitals will be recruited.

5 Data collection

Baseline characteristics for both hospital and patients were collected. For hospital characteristics, data were collected at the beginning of the study. These included: level of hospital, hospital capacity (number of beds, number of medical personnel, number of outpatient services, number of emergency services), and relevant facilities (including cardiac

catheterization room and hospital information system).

For each patient enrolled into the study, the following information will be collected:

- socio-demographic variables (income, working class status, education);
- symptoms and signs relating to the presenting ACS;
- medical history, electrocardiographic and biomarker findings;
- details of investigations performed;

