6.5 Analysis for in-hospital all-cause mortality (secondary outcome)

For the analysis of in-hospital all-cause mortality, we will use a similar analysis strategy and similar models to the primary outcomes.

The raw percentage of in-hospital all-cause mortality will be summarized as n (%) by wedge and cycles (**Table 9**) and by intervention and control (**Table 9.1**).

Repeat model 1 to model 4 for in-hospital all-cause mortality, the resulting odds ratios (or coefficients) of all the fixed effects from Model 1 to Model 3 (unadjusted and adjusted), as well as their 95% CIs, will be reported along with their respective p-values in **Tables 10-12**.

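### Covariates for the secondary adjusted analyses are to be chosen by P<0.05 against the trial's own outcomes, or by undefined clinical judgement, instead of from a list fixed in advance

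*SAP*

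**What the plan says.** Under the confounder paragraph of section 6.4, the SAP states: "All models will have unadjusted analysis and adjusted analysis for the patient-level covariates or hospital-level covariates". It lists no covariates. Selection begins with "Exploratory analysis on covariates (eg. univariate modeling" and scatter plots as the examples given. The entry rule admits "only those that are either significantly associated with the outcomes", with P<0.05 as the threshold, or that are held to be clinically important. It continues: "Potential interaction terms between them will be also examined similarly afterwards".

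The same paragraph limits the weight of these results: "All adjusted analyses will be considered as secondary". The primary analysis is Model 2, with intervention and categorical cycle only.

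The approach carries over to other endpoints. For in-hospital death, section 6.5 says "we will use a similar analysis strategy and similar models to the primary outcomes". Sections 6.6 to 6.8 plan adjusted results for the KPI composite score, the 16 KPIs and the 6-month endpoint. Section 6.10 repeats adjusted Model 2 in the sensitivity analyses for MACE, death and the composite score. Section 6.1 makes no adjustment for multiplicity.

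**The concern.** This is a stated method, not a detail left to another document, and it has four weaknesses.

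- **It cannot be carried out until outcomes are available.** Section 1 undertakes to finalise the SAP before any unblinded analysis, but this rule leaves the content of the adjusted models open past that point. Nothing says that the screen will be done without sight of the intervention effect.
- **It tests the wrong thing.** The stated purpose is to deal with confounding from baseline characteristics, yet entry depends on association with outcome. Imbalance between intervention and control plays no part.
- **It can miss hospital-level confounders.** With about 100 hospitals, a P value for a hospital characteristic is a weak guide to whether the characteristic matters.
- **The intervals take no account of the search.** The adjusted odds ratios and their 95% CIs will be reported as if the model had been fixed.

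The clinical-importance route does not repair this, because neither the variables nor the criterion is given.

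In this design the proportion of patients under intervention rises with calendar time. Cycle terms absorb case-mix drift common to all hospitals. They do not absorb a shift that follows the intervention itself, for instance in which patients receive an ACS final diagnosis (section 6.2 restricts the analysis to these). Covariate adjustment is the planned analysis that could bear on such a shift, so its content should not be open.

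**Working it through.** The SAP gives no figure for this point beyond the 0.05 threshold, so there is nothing of its own to reproduce. The steps below show how the rule would behave. Assumed inputs are marked.

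**Inputs from the SAP.** 25,000 patients and 104 hospitals (section 2); 8% event rate and intra-class correlation 0.10 (section 4); two-sided 0.05 (section 6.1).

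**1. Reach.** MACE 1 + death 1 + composite score 1 + KPIs 16 + 6-month endpoint 1 = 20 outcomes with adjusted results.

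**2. Noise admitted.** With K candidates unrelated to the outcome (K assumed), the expected number entering is 0.05K and the chance of at least one is 1 − 0.95^K.

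| K | expected | at least one |
|---|---|---|
| 10 | 0.5 | 40% |
| 20 | 1.0 | 64% |
| 30 | 1.5 | 79% |
| 40 | 2.0 | 87% |

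**3. Chance that a real predictor passes.** Assume a binary covariate with prevalence 0.5.

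- Patient level: SE(log OR) ≈ 1/√(25,000 × 0.08 × 0.92 × 0.25) = 1/√460 = 0.0466.
  - OR 1.1: Φ(0.0953/0.0466 − 1.96) ≈ 0.53.
  - OR 1.2: Φ(0.1823/0.0466 − 1.96) ≈ 0.97.
- Hospital level: multiply the SE by √[1 + (m − 1) × ICC], where m = 25,000/104 = 240.4. At ICC 0.10 the factor is √24.94 = 4.99 and the SE is 0.233.
  - OR 1.2: Φ(0.1823/0.233 − 1.96) ≈ 0.12.
  - The same covariate gives 0.19 at ICC 0.05 and 0.56 at ICC 0.01.

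The screen therefore keeps almost any patient-level variable of moderate effect, is close to a coin toss for weak ones, and drops most hospital-level ones unless the ICC is far below the planning value.

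**4. Do the sets differ between outcomes, and does it move the estimate?** A simulation of 40 replicates used 104 hospitals × 5 cycles × 48 = 24,960 patients. Assumptions: 20 independent patient-level candidates of 30% prevalence (6 with no effect, 7 with OR 1.08, 7 with OR 1.25); MACE about 8%; deaths a random 60% of MACE (4.8%); no intervention effect.

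- Between 6 and 12 covariates were selected for MACE.
- The MACE and death sets were identical in 15% of replicates and differed by 2.2 covariates on average.
- The intervention log OR moved by 0.0012 on average (maximum 0.0050) between the selected and full sets, against a sampling SD of 0.090. That is 0.0012/0.090 = 1.3% of an SD on average and 0.0050/0.090 = 5.6% at most.

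**5. Interactions.** Take the text as meaning interactions among the covariates carried forward. With 6 to 12 of them there are 6 × 5/2 = 15 to 12 × 11/2 = 66 pairs. If all pairs are tested and none is real, 0.75 to 3.3 enter by chance per outcome.

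**6. Cost of a fixed list.** 25,000 × 0.08 = 2,000 expected events. A list of 20 to 30 terms leaves 100 to 67 events per term.

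**The case against.** The adjusted analyses are declared secondary. Primary Model 2 is specified without selected covariates, and section 6.4 reports unadjusted and adjusted results of Models 1 to 3 together. A reader might infer that the rule lets the trial's main result be chosen after the fact; the SAP does not support that.

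Patients are recruited consecutively and Model 2 already adjusts for cycle. Every hospital contributes both control and intervention patients, and wedges are randomised. A fixed hospital characteristic can therefore confound mainly through chance imbalance between wedges, which limits the harm from missing one. In the only simulation available the estimate barely moved. These points stand, and they hold the concern at a moderate level. The simulation's covariates were balanced and patient-level by construction, however, so it says nothing about the imbalance that adjustment is meant to address.

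Three stronger readings are tempting and should not be made:

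- **That the set is re-chosen for each of Models 1 to 4.** The screen is tied to the outcomes, not to the models. Even variation between outcomes is a likely consequence, not a stated rule.
- **That the earlier trial measures the harm.** Section 4 reports that the "unadjusted and adjusted intervention effect size was 12% and 59" per cent. This contrasts no adjustment with adjustment. It does not contrast a selected set with a fixed one, and a fixed list could give the same gap.
- **That hundreds of interactions will be searched.** All pairs among 30 assumed candidates would be 30 × 29/2 = 435, but the text speaks of interactions between the covariates added to the model.

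**Conclusion.** The point holds for the secondary adjusted analyses only. Their covariates are selected on the trial's own outcomes or by unspecified judgement. That basis does not match the aim of controlling confounding, is likely to give different sets for different outcomes, can pass over hospital-level confounders, and leaves the intervals unadjusted for the search. It should be corrected, but it does not threaten the primary result.

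The size of any bias in the adjusted odds ratios cannot be derived from the SAP. With balanced patient-level covariates it is negligible. With imbalanced or hospital-level covariates it could be larger and has not been quantified. The selection probabilities rest on the SAP's planning values and on the assumed prevalence and odds ratios. The 15% agreement between sets rests on the simulation's assumed effects.

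**What to change.** Before unblinding, delete the P<0.05 screen and the interaction search from section 6.4. Replace them with a named list, chosen on clinical grounds and written variable by variable with its coding.

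- **Source.** Use pre-treatment data that section 5 says are collected, for example demographics, presenting signs and severity on arrival, medical history, first ECG finding, and hospital capacity. Section 5 names income, working class status and education but not age or sex, so check the list against the case report form. Keep the hospital-level part short, given 104 hospitals.
- **Exclusions.** State that in-hospital treatment, final diagnosis and other variables arising after arrival that the intervention could change are not candidates.
- **Use.** Apply the same list in the adjusted version of each planned model and outcome, and keep province as the third level as already planned.

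The cost is a few lines of wording and less analysis work than now planned. The downside is that some weak covariates stay in the model, with negligible loss of precision at about 2,000 expected events.
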